#### 9.2.4.1.2. Secondary Analyses

Secondary effectiveness endpoints are listed in Section 2 and Section 7.2.

If sample size permits, subgroup analyses by patient risk category at enrollment, patient age, prior treatment status and performance status at enrollment will be performed, as follows:

- Elderly patients (< 65 years and  $\ge$  65 years)
- ECOG status at enrollment (< 2 and  $\ge 2$ )
- Risk categorization (by MSKCC, Motzer 1999) (poor, intermediate, favourable/good)
- Risk categorization (according to Heng criteria; Heng 2009) (poor, intermediate, favourable/good)
- Treatment naïve patients vs. cytokine pre-treated patients (first line vs. second line)

Further details will be provided in the RAP. Additional subgroups may be pre-specified in the RAP, if appropriate based on new information on the disease or medication under study.

Sufficient baseline information will be captured in order to programmatically characterize patients based on the inclusion/exclusion criteria from the pivotal Phase III clinical trial (VEG105192). If sample size permits, the primary effectiveness, safety and RDI will be evaluated within this population of patients, and the clinical trial eligible population within the study will be compared to the non-clinical trial eligible population within the study. Further details will be provided in the RAP.

If sample size permits, exploratory analyses of duration of response and time to response will be summarized descriptively for the MD population using Kaplan-Meier medians and quartiles. Only the subset of patients who show a confirmed complete or partial tumor response will be included. Censoring rules for duration of response will follow the rules for PFS outlined in detail in the RAP.

In addition, an analysis of the time to scheduled assessments will also be performed to evaluate consistency across sites and the differences between clinical trial and real world assessments. Details will be provided in the RAP.

#### 9.2.4.2. Safety Analyses

Safety endpoints are described in Section 2 and Section 7.3.

The AT population will be used for the analysis of safety data. Complete details of the safety analyses will be provided in the RAP.

## 9.2.4.2.1. Extent of Exposure

The number of patients administered study treatment will be summarized according to the duration of therapy. Average daily dose and duration of treatment (with and without interruptions) and RDI will be summarized. The number and proportion of patients treated with various initial and subsequent dose regimens and changes in treatment patterns over time will be summarized. Discontinuations, and primary reasons for treatment and/or study discontinuation, will also be described.

#### 9.2.4.2.2. Adverse Events

Adverse events (AEs) will be coded using the standard Medical Dictionary for Regulatory Activities (MedDRA) and grouped by system organ class. AEs will be graded by the investigator according to the NCI-CTCAE (version 4.0).

Events will be summarized by frequency and proportion of total patients, by system organ class and preferred term. Separate summaries will be given for all AEs, drugrelated AEs, serious AEs and AEs leading to discontinuation of study treatment.

Characteristics (e.g. number of occurrences, action taken, grade, etc) of the following AEs of special interest will be summarized separately:

- Any adverse event that results in a pazopanib dose modification or discontinuation
- Any other reports of the following AEs:
  - Evidence of liver toxicity (e.g., increased ALT and/or AST, liver failure)
  - New onset or worsened hypertension
  - Cardiac dysfunction
  - Thyroid dysfunction
  - The incidence of deaths and the primary cause of death will be summarized

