Angiogenesis, the process of new blood vessel formation, plays an important role in the development of malignancy as well as the growth and progression of metastatic lesions. The molecular pathways involved in angiogenesis have been targeted for anti-tumor therapy which aim to either block the pathways that regulate HIF $\alpha$  levels, directly inhibit the function of VEGF, or interrupt signaling downstream from the VEGF receptor via tyrosine kinase inhibitors (TKIs). The TKIs inhibit VEGF and PDGF receptors on cancer cells, vascular endothelial cells, and pericytes, stopping the proliferation of tumour cells and the development of tumour blood vessels. One of the first oral TKIs made commercially available as a first line treatment for mRCC in 2006 was sunitinib (Sutent, Pfizer). Although sunitinib is considered an effective treatment, it is associated with a number of adverse events as a result of its toxicity (including hypertension, fatigue, diarrhoea, and hand-foot syndrome) [Schwandt, 2009], which can lead to substantial issues such as incomplete dosing or complete discontinuation.

VOTRIENT™ (pazopanib), a recently approved TKI, is a potent, selective, multitargeted inhibitor of VEGF receptors (VEGFR) 1, 2, and 3; PDGF receptors α and β; and stem cell factor receptor (c-Kit) [Sonpavde, 2007; Sonapavde, 2008]. It has been demonstrated to be a more selective kinase inhibitor than sunitinib with a higher binding affinity for VEGFR-2 in vitro [Karaman, 2008; Kumar, 2009]. In a pivotal Phase 3, randomized, double-blind trial [VEG105192], pazopanib when compared with placebo showed a statistically significant improvement in median progression-free survival (PFS) of approximately 8 months (10.8 versus 2.9 months [Independent Review Committee assessment, HR 0.36, 95% CI 0.24 to 0.55]) [Sternberg, 2010]. Pazopanib was associated with a significant improvement in objective response rate (ORR: complete response [CR] + partial response [PR]) compared with placebo (32% vs. 4%; p<0.001) as well as a clinically relevant reduction in risk of death. The most commonly reported adverse events in patients treated with pazopanib during the study were diarrhoea, hypertension, hair color changes, nausea, anorexia, vomiting and fatigue [for additional details, refer to local labeling for pazopanib].

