# 7.4.2.3. Laboratory and Other Safety Assessment Abnormalities Reported as AEs and SAEs

Any abnormal laboratory test results (hematology, clinical chemistry, or urinalysis), or other safety assessments (e.g., ECGs, radiological scans, vital signs measurements) including those that worsen from baseline, and events felt to be clinically significant in the medical and scientific judgment of the investigator are to be recorded as an AE or SAE, in accordance with the definitions provided.

In addition, an associated AE or SAE is to be recorded for any laboratory test result or other safety assessment that led to an intervention, including permanent discontinuation of study treatment, dose reduction, and/or dose interruption/delay.

Any new primary cancer must be reported as an SAE.

However, any clinically significant safety assessments that are associated with the underlying disease, unless judged by the investigator to be more severe than expected for the patient's condition, are not to be reported as AEs or SAEs.

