#### 7.4.2.5. Time Period and Frequency of Detecting AEs and SAEs

The investigator or site staff is responsible for detecting, documenting and reporting events that meet the definition of an AE or SAE.

SAEs and AESIs will be collected from the time the first dose of study treatment is administered until 30 days following discontinuation of pazopanib regardless of initiation of a new cancer therapy or transfer to hospice.

In addition, any SAE assessed **as related** to pazopanib or a GSK concomitant medication must be recorded from the time a patient consents to participate in the study up to and including any follow-up contact. All SAEs will be reported to GSK within 24 hours, as indicated in Section 7.4.2.6.

After discontinuation of study treatment, to the extent feasible, the investigator should monitor all AESIs/SAEs that are ongoing until resolution or stabilization of the event or until the patient is lost to follow-up.

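### Section 9.2.4.2.2 promises percentages for all AEs and drug-related AEs, but only SAEs and AESIs are systematically collected

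*Protocol*

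**What the plan says.** On analysis, Section 9.2.4.2.2 says: "Events will be summarized by frequency and proportion of total patients, by system organ class and preferred term". It continues: "Separate summaries will be given for all AEs", and the same sentence goes on to name drug-related AEs, serious AEs and those that led to discontinuation. The AESIs are then summarised separately, with characteristics such as grade and action taken.

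On collection, Section 7.4.2.5 sets the window: "SAEs and AESIs will be collected from the time the first dose of study treatment is administered until 30 days following discontinuation of pazopanib". Primary objective 5 (Section 2), the adverse event row of Table 1, the baseline list (Section 7.1.1) and the follow-up list (Section 7.2) name the same two classes. Section 7.4.1 defines an AESI in two parts. The first is any AE that caused a pazopanib dose modification or discontinuation. The second is liver toxicity, new or worsened hypertension, cardiac dysfunction or thyroid dysfunction, at any severity.

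The protocol also contains broader wording. Section 7.4.2.5 opens with "The investigator or site staff is responsible for detecting, documenting and reporting events that meet the definition of an AE or SAE", and Section 7.4.2 says much the same. Section 7.4.2.3 says that clinically significant laboratory and other safety abnormalities "are to be recorded as an AE or SAE, in accordance with the definitions provided". Section 7.4.3 requires certain pregnancy outcomes to be reported as an AE or SAE.

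**The concern.** A percentage of total patients, by preferred term, in a table labelled as all AEs is normally read as incidence on treatment. That reading needs every AE to be sought and recorded in every patient. Here a non-serious event outside the AESI definition has no row in Table 1, no entry in the baseline or follow-up lists, and no collection window. Whether it reaches the database depends on whether a site follows the specific items or the general sentences. The denominator is everyone treated, while the numerator is complete for some event types and partial for others, and the table does not show which.

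Tolerability is one of the stated reasons for the study (Section 1.2), so readers are likely to look at these tables for the common, mostly non-serious toxicities. Those are the events the collection rules cover least well.

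**Working it through.** No sample size, power or rate is involved, so the check sets the planned tables against the collection rules and then counts the affected toxicities.

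**Step 1: each planned table against what is collected.**

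| Table in Section 9.2.4.2.2 | Collected systematically? | Basis |
|---|---|---|
| Serious AEs | Yes | Objective 5; Table 1; Sections 7.1.1, 7.2, 7.4.2.5 |
| AEs leading to discontinuation | Yes | First part of the AESI definition, Section 7.4.1 |
| AESIs | Yes | Section 7.4.1; Table 1; Section 7.4.2.5 |
| All AEs | Only the part that is an SAE or AESI | No item or window covers the rest |
| Drug-related AEs | Only the part that is an SAE or AESI | Same |

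**Step 2: does the general wording close the gap?** Section 7.4.2.1 defines an AE broadly. A site that takes the opening sentence of Section 7.4.2.5 literally would report any such event. A site that works from Table 1 would report SAEs and AESIs. If all sites follow Table 1, other non-serious events are absent. If sites differ, the percentages depend partly on the mix of readings, and Section 9.2.4 pools all centres before analysis. In neither case is the all-AE percentage an incidence.

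**Step 3: which known toxicities are affected?** Section 1.1 says of the Phase III trial: "The most commonly reported adverse events in patients treated with pazopanib during the study were diarrhoea, hypertension, hair color changes, nausea, anorexia, vomiting and fatigue". Matching the seven terms to Section 7.4.1:

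- AESI by type at any severity: hypertension. That is 1 of 7.
- Not an AESI by type: diarrhoea, hair colour changes, nausea, anorexia, vomiting, fatigue. That is 7 − 1 = 6 of 7. Each is systematically captured only if serious or if it led to dose modification or discontinuation.

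**Step 4: size.** The protocol gives neither the true incidence of these six events in this population nor the fraction that would be serious or change dosing, so the shortfall cannot be derived. As an illustration on assumed figures only:

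- Reported percentage = true incidence × capture fraction.
- With 700 patients and an assumed true incidence of 50%, 700 × 0.50 = 350 patients have the event.
- If 10% are captured, 350 × 0.10 = 35 patients, and 35/700 = 5%.
- If 50% are captured, 350 × 0.50 = 175 patients, and 175/700 = 25%.

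The illustration shows only that the reported figure scales directly with an unknown capture fraction.

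**The case against.** **The safety objective is intact.** Objective 5 concerns SAEs and AESIs, and Section 9.2.4.2.2 summarises these and the AEs leading to discontinuation. This stands: the defect is confined to two additional tables.

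**All AEs may simply mean all AEs collected, and details are left to the RAP (Section 9.2.4.2).** This stands in part. The sponsor may intend that meaning, and the RAP can change titles and footnotes. But the protocol does not say so, it defines an AE broadly, and it commits to these tables. A RAP cannot recover events that were never recorded, and conflicting site instructions act while data are being collected.

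**Capture is wider than a count of 1 in 7 suggests.** The first part of the AESI definition takes in any type and grade of AE that changed dosing, and fatigue is also measured by the FACIT Fatigue scale where questionnaires are permitted. Both are true. The count says which events are exposed to incomplete capture, and it does not measure a bias. Mild and moderate events that did not change dosing remain outside, and a scale score does not supply a preferred-term count.

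**Variation between sites is not documented.** Also fair. Methods for detecting and recording AEs are placed in the Study Procedures Manual, which is not available here and may settle the matter. The conflict in the protocol text remains.

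**A stronger reading to avoid.** Because secondary objective 1 evaluates safety in patients resembling those in VEG105192, a reader might infer that AE rates will be set against that trial and that pazopanib will look better tolerated than it is. The documents do not support this. Section 9.2.4.1.2 compares trial-eligible with non-eligible patients inside this study, under the same collection rules. Objective 3 compares baseline characteristics with a trial population, and Section 9.2.2.1 says there are no treatment comparisons.

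**Conclusion.** The point holds in a limited form. Two of the planned summaries, all AEs and drug-related AEs as a proportion of total patients, are not supported by the systematic collection rules. For six of the seven common toxicities named in Section 1.1, the percentages would be incomplete and, read as incidence, too low. The direction follows from the collection rules, but the size cannot be derived from the protocol.

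This rests on two assumptions: that the specific collection items govern what sites record, or that sites differ in how far they go beyond them; and that readers take a percentage of total patients as incidence. If every site recorded every AE, the shortfall would disappear, but nothing in Table 1 or the visit lists provides for that. Hypertension, the other named AESIs, serious events and events that changed dosing are not affected.

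**What to change.** In Section 9.2.4.2.2:

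- Replace the all-AE and drug-related-AE summaries with summaries of all SAEs and AESIs, and of drug-related SAEs and AESIs.
- State that other non-serious AEs are not systematically collected.
- Report no overall AE incidence.
- List any other AEs that sites report, without a percentage.

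Reconcile Sections 7.4.2, 7.4.2.3, 7.4.2.5 and 7.4.3 with Table 1 and Section 7.4.1, so that sites can tell which events are systematically collected and which may be reported in addition. This should not be done by telling sites to record SAEs and AESIs only. That would cut safety reporting and clash with the laboratory wording in Section 7.4.2.3 and the pregnancy reporting in Section 7.4.3.

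The cost is wording in five sections and the table titles, with no new data. Extending collection to all AEs would also remove the mismatch, but it would add data collection in a study that Section 7 says is designed to keep the burden on sites and patients low.

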# 9.2.4.2.3. Clinical Laboratory Evaluations

Laboratory testing performed locally as part of routine practice and reported in the CRF will be summarized. All data will be reported according to the nominal visit date for which it was recorded (i.e. no visit windows will be applied). Further details will be provided in the RAP.

#### 9.2.4.3. Relative Dose Intensity

Relative dose intensity will be summarized as proportion of patients with reduced RDI and by median (range), and its relationship with treatment outcomes will be evaluated using appropriate regression methods. Multiple logistic regression will also be applied to identify factors potentially influencing RDI. These analyses will be repeated for the subgroups, where relevant.

#### 9.2.4.4. Health Outcomes Analyses

Health-related quality of life (HRQoL) will be assessed using the EQ-5D (3L) Index and VAS, the FKSI-19 and the FACIT Fatigue scale.

The EQ-5D questionnaire will be completed at baseline and approximately every three months until study discontinuation/completion. Frequency of assessments will depend on the particular study. Two scores will be estimated – the utility score calculated from the 5 domains using a scoring algorithm and the VAS score based on the 0-100 feeling thermometer. Changes from baseline will be summarised and at specified timepoints of interest. The calculation of scores and methods to deal with missing data will be handled according to the questionnaire's standard scoring guidelines.

The FKSI-19 and FACIT Fatigue scale will be completed at baseline, and approximately every three months until study discontinuation/completion. Changes from baseline will be summarised and at specified timepoints of interest will be analysed. The calculation of scores and methods to deal with missing data will be handled according to the questionnaire's standard scoring guidelines. Full details of all the health outcomes analyses will be provided in the RAP.

#### 10. STUDY CONDUCT CONSIDERATIONS

## 10.1. Posting of Information on Clinicaltrials.gov

Study information from this protocol will be posted on clinicaltrials.gov before enrolment of patients begins.

## 10.2. Regulatory and Ethical Considerations, Including the Informed Consent Process

This non-interventional study will be conducted in accordance with the Guidelines for Good Pharmacoepidemiology Practices (GPP) issued by the International Society for Pharmacoepidemiology (ISPE). Data protection and privacy regulations will be strictly observed in capturing, forwarding, processing, and storing patient data.

The study will be conducted in accordance with ICH Good Clinical Practice (GCP) (as they apply to observational research), all applicable patient privacy requirements, and the ethical principles that are outlined in the Declaration of Helsinki 2008, including, but not limited to:

- Institutional Review Board (IRB)/Independent Ethics Committee (IEC) review and approval of study protocol and any subsequent amendments
- Patient informed consent
- Investigator reporting requirements

GSK will provide full details of the above procedures, either verbally, in writing, or both. Written informed consent must be obtained from each patient prior to participation in the study.

## 10.3. Quality Control (Study Monitoring)

In accordance with applicable regulations, GCP, and GSK procedures, the site will be contacted prior to the start of the study to review with the site staff the protocol, study requirements, and their responsibilities to satisfy regulatory, ethical, and GSK requirements. When reviewing data collection procedures, the discussion will include identification, agreement and documentation of data items for which the CRF will serve as the source document.

Data quality will be confirmed through a series of programmed data quality checks that automatically detect out-of-range or anomalous data, as detailed in the study data monitoring plan. Full details will be provided in the clinical monitoring plan, including

for-cause monitoring that is appropriate for the study design. The investigator and the head of the medical institution (where applicable) agrees to allow the monitor direct access to all relevant documents and to allocate their time and the time to their staff to monitor to discuss findings and any issues.

Monitoring will be conducted in a manner to ensure that the:

- Data are authentic, accurate, and complete
- Safety and rights of patients are being protected
- Study is conducted in accordance with the currently approved protocol and any other study agreements and all applicable regulatory requirements

## 10.4. Quality Assurance

To ensure compliance with all applicable regulatory requirements, GSK may conduct quality assurance audits of the site. Regulatory agencies may conduct a regulatory inspection at any time during or after completion of the study. In the event of an audit or inspection, the investigator (and institution) must agree to grant the auditor(s) and inspector(s) direct access to all relevant documents and to allocate their time and the time of their staff to discuss any findings/relevant issues.

## 10.5. Study and Site Closure

Upon completion or termination of the study, the monitor will conduct site closure activities with the investigator or site staff (as appropriate), in accordance with applicable regulations and GSK Standard Operating Procedures.

GSK reserves the right to temporarily suspend or terminate the study at any time for reasons including (but not limited to) safety issues, ethical issues, or severe noncompliance. If GSK determines that such action is required, GSK will discuss the reasons for taking such action with the investigator or head of the medical institution (where applicable). When feasible, GSK will provide advance notice to the investigator or head of the medical institution of the impending action.

If a study is suspended or terminated, GSK will promptly inform all investigators, heads of the medical institutions (where applicable),and/or institutions conducting the study. GSK will also promptly inform the relevant regulatory authorities of the suspension/termination along with the reasons for such action. Where required by applicable regulations, the investigator or head of the medical institution must inform the IRB/IEC promptly and provide the reason(s) for the suspension/termination.

GSK may close sites which fail to recruit within a predefined timeframe, as defined within the Study Procedures Manual.

#### 10.6. Records Retention

Following closure of the study, the investigator or head of the medical institution (where applicable) must maintain all site study records (except for those required by local

regulations to be maintained elsewhere) in a safe and secure location. The records must be easily accessible when needed (e.g., for a GSK audit or regulatory inspection) and must be available for review in conjunction with assessment of the facility, supporting systems, and relevant site staff.

Where permitted by local laws/regulations or institutional policy, some or all of the records may be maintained in a format other than hard copy (e.g., microfiche, scanned, electronic); however, caution must be exercised before such action is taken. The investigator must ensure that all reproductions are legible and are a true and accurate copy of the original. In addition, they must meet accessibility and retrieval standards, including regeneration of a hard copy, if required. The investigator must also ensure that an acceptable back-up of the reproductions exists and that there is an acceptable quality control procedure in place for creating the reproductions.

GSK will inform the investigator of the time period for retaining the site records in order to comply with all applicable regulatory requirements. The minimum retention time will meet the strictest standard applicable to a particular site, as dictated by local laws/regulations, GSK standard operating procedures, and/or institutional requirements.

The investigator must notify GSK of any changes in the archival arrangements, including, but not limited to archival of records at an off-site facility or transfer of ownership of the records in the event that the investigator is no longer associated with the site.

